Grade 4	
 • Monitor closely • Provide supportive care according to institutional standards 	
1st occurrence:
 
 • Interrupt PDR001/placebo and dabrafenib and trametinib. • Permanently discontinue PDR001/placebo. If benefit risk assessment support treatment continuation, re-start PDR001/placebo. Dabrafenib and trametinib may be reinitiated at the next lower dose per Table 6-7. Re-escalation of the subject's dose is recommended if criteria in Section 6.3.2 are met. • For asymptomatic amylase and/or lipase* elevation, if AE resolves to ≤ Grade 1 or baseline within 4 weeks, subject can resume treatment with PDR001/placebo, otherwise PDR001/placebo must be permanently discontinued. 
2nd occurrence:
 
 • Permanently discontinue PDR001/placebo, dabrafenib and trametinib. • For asymptomatic amylase and/or lipase* elevation, if AE resolves to ≤ Grade 1 or baseline within 4 weeks, subject can resume treatment with PDR001/placebo only if subject is deriving benefit and after approval by both the investigator and the Medical Monitor, otherwise PDR001/placebo must be permanently discontinued. Dabrafenib and trametinib may be reinitiated at the next lower dose per Table 6-7. Re-escalation of the subject's dose is recommended if criteria in Section 6.3.2 are met. • Asymptomatic amylase and/or lipase elevation in the absence of clinical evidence of pancreatitis. This includes negative radiographic evaluation as well as absence of clinical symptoms of pancreatitis.

6.3.3.12 Mandatory dose modifications and recommended clinical management guidelines for other adverse events of special interest

Guidelines for mandatory dose modifications and clinical management of “other” AEs are provided in [Table 6-19](#). Under the category of “other” are several AEs of special interest that must be managed specifically. “Other” AEs included in this section are: autoimmune neuropathy, demyelinating polyneuropathy, Guillain-Barre, myasthenia Gravis-like syndrome,

non-infectious myocarditis, non-infectious pericarditis, pancreatitis and, rapid onset of Grade 3 fatigue in the absence of disease progression.

Table 6-19 Mandatory dose modifications and recommended clinical management guidelines for other AEs of special interest

Other: Autoimmune neuropathy, demyelinating polyneuropathy, Guillane-Barré, Myasthenia Gravis-like syndrome, Non-infectious myocarditis, pericarditis, pancreatitis (for asymptomatic amylase and/or lipase elevations refer to Table 6-18), and Grade 3 Fatigue with rapid onset in absence of disease progression

Grade	Recommended adverse event management guidelines	Mandatory dose modification requirements
Mild (Grade 1)	
 Provide symptomatic treatment 	
 Continue PDR001/placebo, dabrafenib and trametinib at the same dose.
Moderate (Grade 2) or Grade 1 that does not improve with symptomatic treatment	
 Provide symptomatic treatment. Systemic corticosteroids may be indicated. Recommend biopsy for confirmation of diagnosis. A specialist should be consulted. 	
1st occurrence:
 
 Interrupt PDR001/placebo and dabrafenib and trametinib until recovery to \leq Grade 1 or baseline. 
 Restart PDR001/placebo at the same schedule. Continue dabrafenib and trametinib at the same dose. AE resolution to \leq Grade 1 or baseline must occur within a period of 12 weeks since event has been identified, otherwise PDR001/placebo must be permanently discontinued. 
2nd occurrence:
 
 Permanently discontinue PDR001/placebo. Interrupt dabrafenib and trametinib until recovery to \leq Grade 1 or baseline, dabrafenib and trametinib may be reduced to the next lower dose per Table 6-7. Re-escalation of the subject's dose is recommended if criteria in Section 6.3.2 are met. 
3rd occurrence:
 
 Interrupt dabrafenib and trametinib until toxicity resolves to \leq Grade 1 or baseline, then reduce dabrafenib and trametinib to the next lower dose level per Table 6-7. Re-escalation of the subject's dose is recommended if criteria in Section 6.3.2 are met. 
4th occurrence:

Other: Autoimmune neuropathy, demyelinating polyneuropathy, Guillane-Barré, Myasthenia Gravis-like syndrome, Non-infectious myocarditis, pericarditis, pancreatitis (for asymptomatic amylase and/or lipase elevations refer to [Table 6-18](#)), and Grade 3 Fatigue with rapid onset in absence of disease progression

Grade	Recommended adverse event management guidelines	Mandatory dose modification requirements
Severe (Grade 3)	
 All management for moderate irAEs Initiate systemic corticosteroids (prednisone or equivalent) at a dose of 1-2 mg/kg QD. 	
 Permanently discontinue dabrafenib and trametinib. 
1st occurrence:
 
 Interrupt PDR001/placebo, dabrafenib and trametinib until recovery to ≤ Grade 1 or baseline 
 Restart PDR001/placebo at the same schedule. Dabrafenib and trametinib may be reduced to the next lower dose per Table 6-7. Re-escalation of the subject's dose is recommended if criteria in Section 6.3.2 are met. AE resolution to ≤ Grade 1 or baseline must occur within a maximum period of 12 weeks since a Grade 3 event has been identified, otherwise PDR001/placebo must be permanently discontinued. 
2nd occurrence:
 
 Permanently discontinue PDR001/placebo and consider reducing dabrafenib and trametinib to the next lower dose per Table 6-7. Re-escalation of the subject's dose is recommended if criteria in Section 6.3.2 are met. 
3rd occurrence:
 
 Permanently discontinue dabrafenib and trametinib.
Grade 4	
 Refer to management of severe AEs 	
 Permanently discontinue PDR001.

6.3.4 Mandatory dose modifications and recommended clinical management guidelines for infusion reactions

Acute infusion reactions (which can include cytokine release syndrome, angioedema, or anaphylaxis) are different from allergic/hypersensitive reactions, although some of the manifestations are common to both AEs. Signs and symptoms usually develop during or shortly after drug infusion and generally resolve completely within 24 hours of completion of infusion.

[figure not shown]

Table 6-20 Mandatory dose modifications and recommended clinical management guidelines for infusion reaction and cytokine release syndromes

Infusion reaction and cytokine release syndrome (NCI-CTCAE v4.03)		
Grade	Recommended Adverse Event management guidelines	Mandatory Dose Modification requirements
Grade 1 infusion reaction or Grade 1 cytokine release syndrome: mild/mild transient reaction; infusion interruption not indicated; intervention not indicated.	Increase monitoring of vital signs as medically indicated until the patient is deemed medically stable in the opinion of the investigator.	
 Continue PRD001/placebo Continue dabrafenib and trametinib at the same dose level.
Grade 2 infusion reaction or Grade 2 cytokine release syndrome: therapy or infusion interruption indicated but responds promptly to symptomatic treatment (e.g., antihistamines, NSAIDs, narcotics, IV fluids); prophylactic medications indicated for ≤ 24 hr	
 Stop Infusion Additional appropriate medical therapy may include but is not limited to: 
 IV fluids Antihistamines NSAIDs Acetaminophen Narcotics Increase monitoring of vital signs as medically indicated until the patient is deemed medically stable in the opinion of the investigator. If symptoms resolve within one hour of stopping drug infusion, the infusion may be restarted at 50% of the original infusion rate (e.g., from 100 mL/hr to 50 mL/hr). Otherwise dosing will be held until symptoms resolve and the patient should be re-premedicated for the next scheduled dose. Patient may be premedicated 1.5 hr (± 30 minutes) prior to infusion of PDR001 with: 
 Diphenhydramine 50 mg PO (or equivalent dose of antihistamine). Acetaminophen 500-1000 mg PO (or equivalent dose of analgesic). 	
1st occurrence:
 
 Continue PRD001/placebo treatment with premedication 
2nd occurrence:
 
 Despite premedication or prolongation of infusion, consider permanent discontinuation of PDR001/placebo.
Grade 3 infusion reaction or grade 3 cytokine release syndrome: prolonged (e.g., not rapidly responsive to symptomatic medication and/or brief interruption of infusion); recurrence of symptoms following initial improvement; hospitalization indicated for clinical sequelae	
 Stop Infusion Additional appropriate medical therapy may include but is not limited to: 
 IV fluids Antihistamines NSAIDs Acetaminophen Narcotics 	
 Permanently discontinue PDR001/placebo

Infusion reaction and cytokine release syndrome (NCI-CTCAE v4.03)		
Grade	Recommended Adverse Event management guidelines	Mandatory Dose Modification requirements
(e.g., renal impairment, pulmonary infiltrates) Grade 4: Grade 4 infusion reaction: Life-threatening consequences; urgent intervention indicated OR Grade 4 cytokine release syndrome: Life-threatening consequences; pressor or ventilatory support indicated	
 • Oxygen • Pressors • Corticosteroids • Epinephrine • Increase monitoring of vital signs as medically indicated until the patient is deemed medically stable in the opinion of the investigator. Hospitalization may be indicated. 	

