6.3.1 General dose modification instructions for PDR001 or placebo

No dose reductions are allowed for PDR001. Dose interruption for PDR001/placebo includes delaying or withholding the treatment for any reason as well as an interruption of treatment during an infusion. Subjects with adverse events suspected to be related to PDR001 or placebo including those of potential immune-mediated etiology (irAE) (see definition in [Section 6.3](#)) must be permanently discontinued from PDR001 or placebo if (1) the AE doesn't recover to ≤ Grade 1 or baseline within 12 weeks and/or (2) the dose of steroids (for the management of irAE) remains > 10 mg/day prednisone or equivalent for >12 weeks.

The 12 week timeframe will begin from the time the irAE reaches a grade that leads to PDR001/placebo interruption.

Subjects who discontinue the study for a study related adverse event or an abnormal laboratory value must be followed as described in [Section 7](#).

6.3.2 General dose modification instructions for dabrafenib and trametinib:

[figure not shown]
If treatment related toxicities occur that are specific to combination treatment of dabrafenib and trametinib, then both treatments should be simultaneously dose reduced, interrupted or discontinued with the exceptions shown below:

Exception where dose modification is necessary for **only dabrafenib**:

- Uveitis ([Table 6-25](#))

Exception where dose modifications are necessary for **only trametinib**:

- Retinal vein occlusions (RVO) ([Table 6-25](#)) and retinal pigment epithelial detachment (RPED) ([Table 6-26](#))
- Left ventricular ejection fraction (LVEF) reduction ([Table 6-22](#))

If a subject’s dose of dabrafenib and trametinib has been reduced per the dose modification instructions, re-escalation of the subject’s dose is recommended provided the following criteria are met:

- a period of 4 weeks of treatment has passed since restarting dosing at the lower dose level and there is no recurrence of the AE
- the subject is deriving clinical benefit

For dabrafenib and/or trametinib related adverse events: if following an interruption of dabrafenib and trametinib, an AE doesn’t recover to ≤ Grade 1 or baseline within 4 weeks, dabrafenib and trametinib must be discontinued.

6.3.3 Dose modification and management guideline for adverse events common to PDR001, dabrafenib and trametinib

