6.3.3.6 Mandatory dose modifications and recommended clinical management guidelines for pneumonitis

[figure not shown]
Guidelines for dose modification and management of pneumonitis considered to be related to study treatment by the investigator are provided in [Table 6-13](#).

Table 6-13 Mandatory dose modifications and recommended clinical management guidelines for pneumonitis

Pneumonitis (NCI-CTCAE v4.03)		
Grade	Recommended adverse event management guidelines	Mandatory dose modification requirements
Grade 1: Radiographic changes only- Asymptomatic	
 CT scan (high-resolution with lung windows) recommended, with serial imaging to monitor for resolution or progression- re-image at least every 3 weeks Monitor for symptoms every 2-3 days - Clinical evaluation and laboratory work-up for infection Monitoring of oxygenation via pulse oximetry recommended Consultation of pulmonologist recommended. 	
 Continue dabrafenib and trametinib at the same dose. Interrupt PDR001/placebo, until recovery to baseline. 
 Once recovered, reinitiate PDR001/placebo at the same schedule. If worsens, treat as Grade 2 or 3-4. AE resolution to ≤ Grade 1 or baseline must occur within a period of 12 weeks since Grade 1 event has been identified, otherwise PDR001 /placebo must be permanently discontinued
Grade 2: Symptomatic-medical intervention indicated; limits instrumental ADLs	
 CT scan (high-resolution with lung windows) 	
1st occurrence:
 
 Interrupt PDR001/placebo, and trametinib until recovery to ≤ Grade

Pneumonitis (NCI-CTCAE v4.03)

Grade	Recommended adverse event management guidelines	Mandatory dose modification requirements

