	
 • Monitor symptoms daily, consider hospitalization • Clinical evaluation and laboratory work up for infection • Consult pulmonologist • Pulmonary function tests - if normal at baseline, repeat every 8 weeks • Bronchoscopy with biopsy and/or BAL recommended • Symptomatic therapy including corticosteroids if clinically indicated (systemic corticosteroids at a dose of 1 to 2 mg/kg/day prednisone or equivalent as clinically indicated). 	
1 or baseline. Dabrafenib may continue at the same dose.
 
 • Once recovered, reinstate PDR001/placebo at same schedule and reduce trametinib to the next lower dose per Table 6-7. Re-escalation of the subject's dose is recommended if criteria in Section 6.3.2 are met. • If no recovery to \leq Grade 1 within 4 weeks, permanently discontinue trametinib. Dabrafenib may continue. • AE resolution to \leq Grade 1 or baseline must occur within a period of 12 weeks since Grade 2 event has been identified, otherwise PDR001/placebo must be permanently discontinued. • If worsens treat as Grade 3 or 4. 
2nd occurrence:
 
 • Permanently discontinue PDR001/placebo. • Interruption of trametinib until recovery to Grade 1 or baseline. Dabrafenib may continue at the same dose.

Pneumonitis (NCI-CTCAE v4.03)		
Grade	Recommended adverse event management guidelines	Mandatory dose modification requirements

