6.3.5.8 Mandatory dose modification and management guideline thromboembolic events

Advise patients to immediately seek medical care if they develop symptoms of deep vein thrombosis (DVT) or pulmonary embolism (PE), such as shortness of breath, chest pain, or arm or leg swelling. If any signs or symptoms of venous thromboembolism are present, the subject will undergo specific laboratory and medical imaging studies to confirm it. The medical imaging study or studies selected will depend on the anatomic site or organ of involvement (e.g., Doppler ultrasound, venography, ventilation perfusion lung scan, angiography, MRI). If the diagnosis is confirmed, appropriate medical care according to standard local clinical practice should be initiated immediately.

Permanently discontinue trametinib for life threatening PE. Withhold trametinib for uncomplicated venous thromboembolism for up to 3 weeks; if improved, trametinib may be resumed at a lower dose level.

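### Table 6-13, Grade 1 pneumonitis: the restart test and the 12-week stop test use different recovery levels, so the mandatory stop cannot be triggered

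*Protocol*

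**What the plan says.** The Grade 1 row of Table 6-13 (Section 6.3.3.6) covers radiographic change without symptoms. Its mandatory column gives these instructions:

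- Backbone: "Continue dabrafenib and trametinib at the same dose".
- Hold on the antibody or placebo: "Interrupt PDR001/placebo, until recovery to baseline", after which it is restarted on the same schedule.
- Worsening: "If worsens, treat as Grade 2 or 3-4".
- Stop: PDR001/placebo must be permanently discontinued unless "AE resolution to ≤ Grade 1 or baseline must occur within a period of 12 weeks since Grade 1 event has been identified".

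Two general passages bear on the same event. Section 6.3.1 requires permanent discontinuation of PDR001/placebo if a suspected related event does not "recover to ≤ Grade 1 or baseline within 12 weeks and/or (2) the dose of steroids" used for an immune-related event stays above 10 mg/day prednisone or equivalent for more than 12 weeks. It starts the 12-week clock when the event reaches the grade that leads to interruption. Section 6.1.1.4 says the PDR001/placebo dose may be interrupted for up to 12 weeks. It names no grade and states no consequence if the limit is passed.

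**The concern.** A mandatory stop should separate patients who have recovered by the deadline from those who have not. Here the recovery level in the stop test is no better than the grade that brings a patient into the row, so the test separates nobody. The hold in the same row asks for more, namely a return to baseline. A patient whose radiographic changes persist is caught between the two.

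At stake is whether such a patient counts, at week 12, as interrupted or as permanently off PDR001/placebo. The protocol names pneumonitis as a possible overlapping toxicity of the three drugs (Section 2.6). It also reports discontinuation of any drug because of adverse events as a headline safety result (36.3% versus 17.8%, Section 2.1). Two sites could record the same clinical course differently, and both could point to the protocol.

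**Working it through.** No sample size, event count or error rate enters this point, so there is no figure in the plan to reproduce. The check is a logical one on the rule text.

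**Notation.** Let G be the current grade and take baseline as no pneumonitis (G = 0). That is an assumption, but exclusion criterion 11 bars current pneumonitis or interstitial lung disease. The Grade 1 row governs an event while G ≤ 1.

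- Restart allowed: G = 0 (baseline).
- Stop avoided: G ≤ 1, or baseline, at some time within 12 weeks of the Grade 1 finding.
- Stop triggered: the negation of that line.

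For any event in this row G ≤ 1 holds from day 0, so the stop-avoided condition is met at once and its negation is never true.

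**Every course the event can take:**

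| Course | Restart test | 12-week stop | Result under the row |
|---|---|---|---|
| Baseline reached by week 12 | met | not triggered | restart; the lines agree |
| Grade 1 through week 12 and beyond | not met | not triggered | held, with no end point |
| Grade 1 at week 12, baseline later | met late | not triggered | restart after a hold longer than 12 weeks |
| Rises to Grade 2 or more | not applicable | not applicable | moved to the Grade 2 or Grade 3-4 row |

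Read in isolation, the stop sentence could catch an event that began at Grade 1 and stands at Grade 2 or higher at week 12. The worsening instruction has already sent that event to a row with its own rule, so the Grade 1 row's stop is reached in none of the four courses.

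**Do other passages supply the missing stop?**

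- Section 6.3.1, first limb: same threshold, and the clock also starts at the Grade 1 finding, because that grade already leads to interruption. It is empty for the same reason.
- Section 6.3.1, steroid limb: it can act only if steroids are given, and the Grade 1 row recommends none.
- Section 6.1.1.4: it limits the interruption to 12 weeks but does not say what follows. In the second course the row still requires the hold after week 12, Section 6.1.1.4 no longer allows for it, and no stop has been triggered. In the third course the row permits a restart that lies outside the limit.

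**Comparison with the Grade 2 row (first occurrence).** Hold and stop both refer to Grade 1 or lower, or baseline, and the event enters at Grade 2. It fails the test on day 0 and must improve to pass, so the rule can act. The same sentence loses its effect only where the entry grade is 1.

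**The case against.** The strongest reply is that nobody is put at risk by the wording. PDR001/placebo is held while any radiographic change remains. The row recommends repeat imaging at intervals of no more than 3 weeks and symptom checks every 2 to 3 days, and worsening moves the patient to a stricter row. Section 6.1.1.4 also gives sites a general 12-week limit. Most of this stands. A reader might infer that a stop that does not work means dosing continues through unresolved pneumonitis. The documents do not support that, since the row gives no route to re-exposure before baseline is reached. What the reply leaves open is status at week 12 and the late restart, because Section 6.1.1.4 attaches no consequence to its limit.

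A reader might also infer a second contradiction. Section 6.3.2 says of dabrafenib and trametinib that "both treatments should be simultaneously dose reduced, interrupted or discontinued with the exceptions shown below", and its exceptions omit pneumonitis and thromboembolism. Yet the Grade 2 and Grade 3-4 rows of Table 6-13 act on trametinib while dabrafenib may continue, and Section 6.3.5.8 says "Permanently discontinue trametinib for life threatening PE". The documents do not bear out a contradiction:

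- The joint rule in Section 6.3.2 is limited to toxicities specific to the dabrafenib-trametinib combination.
- The opening of Section 6.3.3 names pneumonitis among events reported with any of the three drugs and says that its guidelines may depart from those for the combination.
- The Grade 1 row continues both oral drugs, so it contains no trametinib-only action.
- For thromboembolic events, Table 6-8 marks trametinib alone, in agreement with Section 6.3.5.8.

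At most, the exception list could cross-refer to the event-specific sections.

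**Conclusion.** The point holds for the Grade 1 row of Table 6-13. Its restart and stop criteria refer to different recovery levels, and its 12-week permanent stop cannot be reached by any event the row governs. Persistent Grade 1 pneumonitis is left neither restarted nor discontinued. Recovery to baseline after week 12 allows a restart that does not fit the 12-week limit in Section 6.1.1.4.

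The size is a matter of logic: the stop is reached in none of the four courses. It cannot be turned into a number of patients. Amendment 7 reports 2 + 1 + 88 = 91 patients still on treatment across the three parts, but not how many of them receive PDR001, and the text at hand gives no pneumonitis count.

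The conclusion rests on reading the row as written, with baseline as absence of pneumonitis and with worsening events handled in the other rows. It says nothing about which recovery level is clinically right.

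**What to change.** Reconcile the hold criterion and the 12-week criterion in the Grade 1 row with each other, and with Sections 6.1.1.4 and 6.3.1, so that a patient with persistent Grade 1 changes has one defined status at week 12 and the handling of recovery after week 12 is stated. The clinical team decides which recovery level and which consequence stand.

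In the same edit, read the Table 6-19 row that admits Grade 1 events unresponsive to symptomatic treatment, since it carries the same 12-week test. Optionally, add a line in Section 6.3.2 referring to the event-specific sections.

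The cost is protocol wording in a table that Amendment 7 already revised. No analysis, sample size or data collection changes.

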6.3.4.1 Guidance for corticosteroids tapering for management of immune-related AEs

Reduce prednisone dose by 2.5 to 5.0 mg decrements every 3–7 days until physiologic dose (5 to 7.5 mg of prednisone per day) is reached. Consider to complete tapering over a period of at least 4 weeks. Slower tapering of corticosteroids therapy may be recommended if the adverse event is not showing improvement. Once corticosteroid tapering is achieved at a level of ≤ 10 mg of prednisone/day (or equivalent), PDR001 can be restarted as indicated in the dose modification tables.

6.3.5 Dose modification and management guideline for adverse events suspected to be related to dabrafenib and/or trametinib

Continue PRD001/placebo.

For adverse events of special interest reported **only for dabrafenib and/or trametinib**, general guidelines for dose modification in [Table 6-21](#) should be followed for dabrafenib and trametinib.

In general, if an AE resolves to Grade 1 or baseline at the reduced dose level, and no additional toxicities are seen after 4 weeks of study treatment at the reduced dose, the dose may be increased to the previous dose level.

A dose reduction below 50 mg BID for dabrafenib or below 1 mg QD for trametinib is not allowed. If a dose reduction below 50 mg BID for dabrafenib is required, dabrafenib will be permanently discontinued but these subjects will be allowed to continue trametinib. If a dose reduction below 1.0 mg QD for trametinib is required, then trametinib will be permanently discontinued, but these subjects will be allowed to continue dabrafenib.

[figure not shown]

Table 6-21 General guidelines for dose modification for adverse events suspected to be related to dabrafenib and/or trametinib treatment

Grade	Recommended adverse event management guidelines	Mandatory dose modification requirements
Grade 1 or Grade 2 tolerable	
 Monitor closely. Provide supportive care according to institutional standards. 	
 Continue dabrafenib and trametinib at the same dose level.
Grade 2 (intolerable) or Grade 3	
 Monitor closely. Provide supportive care according to institutional standards. 	
 Interrupt dabrafenib and trametinib (except for cuSCC, keratoacanthoma, new primary melanoma, and basal cell carcinoma) When toxicity resolves to \leq Grade 1 or baseline, restart dabrafenib and trametinib reduced by one dose level per Table 6-7. If the Grade 2 (intolerable) or Grade 3 toxicity recurs, interrupt dabrafenib and trametinib. When toxicity resolves to Grade 1 or baseline, restart dabrafenib and trametinib reduced by another dose level per Table 6-7. Re-escalation of the subject's dose is recommended if criteria in Section 6.3.2 are met.
Grade 4	
 Monitor closely. Provide supportive care according to institutional standards. 	
 Interrupt dabrafenib and trametinib. Restart with dabrafenib and trametinib reduced by one dose level per Table 6-7 once toxicity resolves to \leq Grade 1 or baseline or permanently discontinue dabrafenib and trametinib at the discretion of investigator.

6.3.5.1 Mandatory dose modification and management guideline for changes in LVEF suspected to be related to dabrafenib and/or trametinib treatment

Decreases of left-ventricular-ejection-fraction (LVEF) have been observed in subjects receiving trametinib monotherapy and in combination with dabrafenib. Therefore, ECHOs must be performed to assess cardiac ejection fraction in regular intervals as outlined in the Visit Evaluation Schedule ([Table 7-1](#), [Table 7-2](#) and [Table 7-3](#)). Dose modification guidance and stopping criteria for LVEF decrease are provided in [Table 6-22](#).

[figure not shown]

Table 6-22 Mandatory dose modification and recommended clinical management for changes in LVEF suspected to be related to dabrafenib and/or trametinib treatment

Left Ventricular Ejection Fraction decrease (NCI-CTCAE v4.03)		
LVEF-drop (%) & clinical symptoms	Recommended adverse event management guidelines	Mandatory dose modification requirements

Asymptomatic: Absolute decrease of >10% in LVEF compared to baseline and ejection fraction below the institution's LLN
	
 Report as SAE. Closely monitoring LVEF via ECHO, repeat ECHO within 2 weeks*. If the LVEF recovers within 4 weeks (defined as LVEF \geqLLN and absolute decrease \leq10% compared to baseline) 
 Repeat ECHO 2, 4, 8 and 12 weeks after re-start; continue in intervals of 12 weeks thereafter. If repeat LVEF does not recover within 4 weeks. 
 Consult with cardiologist Repeat ECHO after 2, 4, 8, 12, and 16 weeks or until resolution 	
 Interrupt trametinib. If the LVEF recovers, restart trametinib reduced by one dose level per Table 6-7 and continue dabrafenib at the same dose level. More than two occurrence, permanently discontinue trametinib. Permanently discontinue trametinib if repeat LVEF does not recover within 4 weeks.

Symptomatic: Resting LVEF 39-20% or >20% absolute reduction from baseline resting LVEF <20%
	
 Report as SAE. Consult with cardiologist. Repeat ECHO after 2, 4, 8, 12, and 16 weeks or until resolution. 	
 Permanently discontinue trametinib. Interrupt dabrafenib Restart dabrafenib if LVEF recovers including resolution of symptoms.

* If ECHO does not show LVEF recovery after 2 weeks, repeat ECHO 2 weeks later.

6.3.5.2 Mandatory dose modification and management guideline for hypertension suspected to be related to dabrafenib and/or trametinib treatment

Increases in blood pressure have been observed in subjects receiving trametinib. For adequate monitoring and management of hypertension, all blood pressure assessments should be performed under the following optimal conditions:

- the subject has been seated with back support, ensuring that legs are uncrossed and flat on the floor
- the subject is relaxed comfortably for at least 5 minutes
- restrictive clothing has been removed from the cuff area and the right cuff size has been selected
- the subject's arm is supported so that the middle of the cuff is at heart level
- the subject remains quiet during the measurement.

In subjects with an initial blood pressure reading within the hypertensive range, a second reading should be taken at least 1 minute later, with the 2 readings averaged to obtain a final blood pressure measurement. The averaged value should be recorded in the eCRF.

Persistent hypertension is defined as an increase of systolic blood pressure (SBP) > 140 mm Hg and/or diastolic blood pressure (DBP) > 90 mm Hg in three consecutive visits with blood pressure assessments from two readings collected as described above. Visits to monitor increased blood pressure can be scheduled independently from the per-protocol visits outlined in the Visit Evaluation Schedule ([Section 7.1](#)). Ideally, subsequent blood pressure assessments should be performed within one week.

Asymptomatic hypertension is defined as an increase of SBP >140 mm Hg and/or DBP >90 mmHg in the absence of headache, light-headedness, vertigo, tinnitus, episodes of fainting or other symptoms indicative of hypertension.

For subjects experiencing an increase in systolic and/or diastolic blood pressure that is persistent and may be associated with the study treatment, recommendations for dose modifications and management of hypertension are described below in [Table 6-23](#).

Table 6-23 Mandatory dose modification and recommended clinical management for hypertension suspected to be related to dabrafenib and/or trametinib treatment

Hypertension (NCI-CTCAE 4.03)		
Severity	Recommended adverse event management guidelines	Mandatory dose modification requirements
(Scenario A) 
 Asymptomatic and persistent^a SBP of >140 and <160 mmHg, or DBP >90 and <100 mmHg, or Clinically significant increase in DBP of 20 mmHg (but still below 100 mmHg). 	
 Adjust current or initiate new antihypertensive medication. Titrate antihypertensive medication(s) during the next 2 weeks as indicated to achieve well-controlled^b BP If BP is not well controlled within 2 weeks, recommended to refer to a specialist and go to scenario (B). 	
 Continue dabrafenib and trametinib at the same dose.
(Scenario B) 
 Asymptomatic SBP ≥160 mmHg, or DBP ≥100 mmHg, or Failure to achieve well-controlled BP within 2 weeks in Scenario A	
 Adjust current or initiate new antihypertensive medication(s). Titrate antihypertensive medication(s) during the next 2 weeks as indicated to achieve well-controlled BP. 	
 Interrupt dabrafenib and trametinib if clinically indicated. Once BP is well controlled, restart dabrafenib and trametinib reduced by one dose level per Table 6-7.

 Symptomatic^c hypertension or Persistent SBP ≥160 mmHg, or DBP ≥100 mmHg, despite antihypertensive medication and dose reduction of study treatment. 	
 Adjust current or initiate new antihypertensive medication(s) Titrate antihypertensive medication during the next 2 weeks as indicated to achieve well-controlled BP. Referral to a specialist for further evaluation and follow-up is recommended 	
 Interrupt dabrafenib and trametinib. Once BP is well controlled, restart dabrafenib and trametinib reduced by one dose level per Table 6-7.

 Refractory hypertension unresponsive to above interventions or hypertensive crisis. 	
 Continue follow-up per protocol. 	
 Permanently discontinue dabrafenib and trametinib.

Hypertension (NCI-CTCAE 4.03)

Severity	Recommended adverse event management guidelines	Mandatory dose modification requirements
a.	Hypertension detected in two separate readings during up to three consecutive visits.	
b.	Well-controlled blood pressure defined as SBP \leq 140 mm Hg and DBP \leq 90 mm Hg in two separate readings during up to three consecutive visits.	
c.	Symptomatic hypertension defined as hypertension aggravated by symptoms (e.g., headache, light-headedness, vertigo, tinnitus, episodes of fainting) that resolve after the blood pressure is controlled within the normal range.	

6.3.5.3 Mandatory dose modification and management guideline for new malignancies suspected to be related to dabrafenib and/or trametinib treatment

New cutaneous malignancies:

Cutaneous squamous cell carcinoma (CuSCC), keratoacanthomas (KA) and new primary melanomas have been observed in subjects treated with dabrafenib and dabrafenib/trametinib combination therapy. These treatment-related lesions should be surgically removed according to institutional practices. Dose modification or interruption of study treatment is not required for cuSCC, KA, or new primary melanoma, however cuSCC and new primary melanoma should be reported as a SAE. In addition, a biopsy of the lesion should be taken, where possible, and submitted for further analyses and a summary of the results submitted to Novartis.

[figure not shown]
Subjects should be instructed to immediately inform their physician if new lesions develop. Skin examination should be performed prior to initiation of study treatment and throughout therapy as detailed in the Visit Evaluation Schedule. Monitoring should continue every month for 6 months following discontinuation of dabrafenib or until initiation of another anti-neoplastic therapy.

New non-cutaneous malignancies:

In vitro experiments have demonstrated paradoxical activation of MAP-kinase signaling in *BRAF* wild type cells with RAS mutations when exposed to *BRAF* inhibitors, which may lead to increased risk of non-cutaneous malignancies in subjects treated with dabrafenib. Cases of RAS-driven malignancies have been seen with *BRAF* inhibitors, including dabrafenib. Subjects should be monitored as clinically appropriate. Consider the benefits and risks before continuing treatment with dabrafenib in subjects with a non-cutaneous malignancy harboring a RAS mutation. No dose modification of trametinib is required when taken in combination with dabrafenib.

Following discontinuation of dabrafenib, monitoring for non-cutaneous secondary/recurrent malignancies should continue for up to 6 months or until initiation of another anti-neoplastic therapy.

New cutaneous and non-cutaneous malignancies that are reported to the Investigator should be reported as an SAE. A biopsy of the new malignancy should be taken, where possible, and submitted for further analyses including RAS mutation status. Testing of these biopsies may include analysis of genomic alterations, which include but not limited to DNA, RNA and protein

analysis of these biopsy specimens, and would analyze the biological pathways known to be associated with, and relevant to, *BRAF*-mutant tumor activation.

6.3.5.4 Mandatory dose modification and recommended clinical management for pyrexia syndrome suspected to be related to dabrafenib and/or trametinib treatment

Episodes of pyrexia syndrome have been observed in subjects receiving dabrafenib monotherapy or in combination with trametinib. The pyrexia syndrome is defined as treatment-related fever ($\geq 38^{\circ}\text{C}$) or chills/rigors/night sweats or flu-like symptoms. In a minority of cases the pyrexia was accompanied by symptoms such as severe rigors/chills, dehydration, hypotension, dizziness or weakness and required hospitalization. The incidence and severity of pyrexia syndrome are increased when dabrafenib is used in combination with trametinib compared to dabrafenib monotherapy.

Dabrafenib and trametinib must be interrupted promptly at the very first symptom of pyrexia or its associated prodrome (chills or rigors or night sweats or flu-like symptoms) and should be restarted upon improvement of symptoms at the same dose if symptom free at least 24 hours.

Subjects should be instructed on the importance of immediately reporting febrile episodes. In the event of a fever, the subject should be instructed to take non-steroidal anti-pyretics as appropriate to control fever. The use of oral corticosteroids should be considered in those instances in which anti-pyretics are insufficient. In subjects experiencing pyrexia associated with rigors, severe chills, dehydration or hypotension, serum creatinine and other evidence of renal function should be monitored carefully during and following severe events of pyrexia.

Pyrexia accompanied by hypotension, dehydration requiring intravenous fluids, renal insufficiency and/or severe (\geq Grade 3) rigors/chills in the absence of an obvious infectious cause should be reported as a SAE.

Guidelines for dose modification and management for pyrexia syndrome considered to be related to dabrafenib are provided in [Table 6-24](#).

Table 6-24 Mandatory dose modification and recommended clinical management for pyrexia syndrome suspected to be related to dabrafenib and/or trametinib treatment

Pyrexia		
Occurrence	Recommended adverse event management guidelines	Mandatory dose modification requirements
